5.4. TIMELINE

Number of Sites: 25

Site Names: Cardiology Departments from Spanish hospitals

Study Start Date: September-2022

Study End Date: December-2024

[figure not shown]
Number of Subjects: 1000 (500 cases and 500 controls)

First Patient In Date: September-2022

Last Patient Out Date: June-2024

Enrollment Period 6 months

Figure 1. Study design and flowchart

6. STATISTICAL ANALYSIS

A minimum sample size of 820 participants (410 per group) was estimated for an expected relative difference in recommendations compliance of the all-or-none composite primary outcome of 20%. An α error of 0.05 and a β error of 0.20 were considered for the sample size. The recommendations compliance was estimated as 42% for women and 52% for men. With the consideration of 20% of lost to follow-up (discontinuations) the total sample size is 984 patients, which is rounded out to 1000 patients (500 women and 500 men). To increase regional representation and allow exploration of potential regional variability, 25 hospitals from all regions in Spain (17 Autonomous Communities) will be invited to participate.

For the description of continuous variables, mean and SD, or median and interquartile range will be used for Gaussian and non-normal distributions, respectively. For describing categorical variables, frequencies and percentages per category will be used. Categorical variables will be compared using the chi² test, whilst continuous variables will be compared using the student *t* test.

Logistic regression models will be used to evaluate differences in binary outcomes between women and men (in hospital AMI management, post discharge MI management). All subjects will be assumed to have a fixed follow-up (12±1 month). Multivariate adjusted models will be used to address any potential confounding in the associations between sex and each of the outcomes. Covariates will be selected based on their pre-defined clinical value and the unbalances observed across groups in the univariate analyses. Linear, multinomial or ordinal regression models would be used in case of continuous, categorical, or ordinal outcomes, respectively.

In addition to the models evaluating the association between sex and outcomes, a predictive model will be conducted to set predictors for the following outcomes:

- 1) a composite of all preventive therapies (all-or-nothing for diet, physical activity, P2Y₁₂ inhibitors, statins, and beta blockers or ACE inhibitors [if prescribed at discharge]), and

- 2) each group of preventive interventions (drugs, cardiac rehab, diet, physical activity)

Candidate predictors are classified as biological factors (age, sex, risk factors, comorbidities), disease-related (type of MI: STEMI/NSTEMI, LVEF, number of vessels...), pharmacological factors (daily number of drugs, daily number of doses, specific drugs), socio-economic factors (zip code, education level, employment status, wages...) and specific gender issues (family responsibilities, work conciliation...). Special consideration will be given to age due to the high figures of in-hospital mortality in young women.

For women-specific analysis, female specific factors (menarche age, pregnancies, gestational diabetes, menopause...) will be considered.

We will use the *Clinical Outcomes, HElthcare REsource UtilizatioN, and related costs* (COHERENT) model to study the hospital-related healthcare resources (ED visits, specialist visits, re-hospitalizations and urgent procedures) and costs.

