4. STUDY DESIGN AND RESEARCH PLAN

4.1. DESIGN.

Prospective, matched cohort study of patients hospitalized for a type 1 AMI with evidence of obstructive coronary artery disease who are discharged home alive. Women will be enrolled first, ideally in a consecutive manner, as they are the focus of the study. Men will be recruited subsequently as the comparison group, with 1:1 matching for age and ECG presentation. Matching will be performed locally, in each study site (hospital). All patients will undergo 1-year follow-up with clinical and therapeutic adherence evaluation.

Reference cohort: 500 women discharged alive after a hospitalization for a type 1 AMI with significant CAD

Comparator cohort: 500 age (± 2 years) and ECG (STEMI/NSTEMI) locally matched men discharged alive after a hospitalization for a type 1 AMI with significant CAD

4.2. RECRUITMENT.

Participant centers

25 hospitals managing routinely AMIs and representing different regions from Spain will be invited to participate

Patient recruitment

All consecutive women fulfilling all inclusion criteria and without exclusion criteria surviving the index hospitalization will be invited to participate. Subsequently, men with inclusion criteria and without exclusion criteria, matched for age and ECG presentation, will be recruited.

Inclusion criteria

- Hospitalization for a type 1 AMI⁶⁹ (detection of a rise and/or fall of cTn value above the 99th percentile URL and with at least one of the followings: symptoms of acute myocardial ischemia; new ischaemic ECG changes; development of pathological Q waves; imaging evidence of new loss of viable myocardium or new regional wall motion

abnormality in a patterns consistent with an ischaemic aetiology; identification of a coronary thrombus by angiography including intracoronary imaging)

- Presence of obstructive coronary artery disease (CAD)⁷⁰ (i.e. coronary artery stenosis $\geq 50\%$)
- Age > 18 years. No maximal age limit applies
- Signed informed consent

Exclusion criteria

- Terminal disease (expected survival < 12 months)
- Unavailable for 12-month follow-up (i.e.: living abroad, social situation...)
- Does not speak Spanish
- Major active comorbidity (severe renal or liver failure, active cancer requiring chemotherapy...), interfering with regular post-MI management

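### The 20% loss allowance is computed as 820 × 1.2 instead of 820 / 0.8, so 1000 enrolled leaves 800 evaluable, below the protocol's own minimum of 820

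*Protocol*

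**What the plan says.** The sample size is set in one paragraph of the protocol, section 6 (Statistical analysis). It opens with the evaluable number: "A minimum sample size of 820 participants (410 per group) was estimated". The assumed rates are given as "The recommendations compliance was estimated as 42% for women and 52% for men", and the error rates as "An α error of 0.05 and a β error of 0.20 were considered for the sample size". The allowance for loss follows: "With the consideration of 20% of lost to follow-up (discontinuations) the total sample size is 984 patients, which is rounded out to 1000 patients". Section 4.1 (Design) and section 5.4 (Timeline) carry the 1000 forward as 500 women and 500 men. Nothing elsewhere in the protocol gives the 20% a meaning other than the share of patients lost.

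**The concern.** If 20% of those enrolled are expected to be lost, the evaluable number is 80% of the enrolled number, so the requirement has to be divided by 0.80. The protocol's 984 looks like a multiplication by 1.20, which covers a smaller loss than the one stated. The later rounding to 1000 might have repaired this by accident, so both totals need checking against 820.

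This paragraph is the only justification given for the size of the study. It tells the reader that 1000 patients secure the required number at 20% loss. If they do not, either the tolerated loss or the power is overstated.

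**Working it through.** **Inputs**, from section 6 unless noted: p₁ = 0.42 (women), p₂ = 0.52 (men), α = 0.05, power = 0.80, loss = 20%, minimum 820, inflated total 984, enrolment 1000. The ratio is 1:1 (section 4.1). The protocol does not state whether the test is two-sided or whether a continuity correction was used, so I tried the variants.

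**Step 1. Reproduce 410 per group.** The difference is d = 0.10 and the mean rate is 0.47. Two-sided, uncorrected:

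n = [1.960 × √(2 × 0.47 × 0.53) + 0.842 × √(0.42 × 0.58 + 0.52 × 0.48)]² / 0.10² = 389.9, so 390 per group (780 in total).

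With the continuity correction:

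n_c = (n / 4) × [1 + √(1 + 4 / (n × d))]² = (389.9 / 4) × [1 + √(1 + 4 / 38.99)]² = 409.6, so 410 per group (820 in total).

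This matches the protocol exactly. One-sided versions give 307 (uncorrected) and 327 (corrected) per group, so neither matches. The 820 is therefore sound on a two-sided, continuity-corrected basis.

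**Step 2. Reproduce 984.** 820 × (1 + 0.20) = 984 exactly, so this is evidently how the allowance was made.

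**Step 3. Inflate correctly.** 820 / (1 − 0.20) = 1025. By group, 410 / 0.80 = 512.5, so 513 per group, or 1026 for equal groups.

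**Step 4. What the stated totals leave.**

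| Enrolled | Left after 20% loss | Against 820 | Largest loss that still leaves 820 |
|---|---|---|---|
| 984 | 984 × 0.80 = 787 | 33 short | 1 − 820/984 = 16.7% |
| 1000 | 1000 × 0.80 = 800 | 20 short | 1 − 820/1000 = 18.0% |
| 1026 | 1026 × 0.80 = 820.8 | met | 20% |

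**Step 5. Power at 400 per group.**

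- Uncorrected: z = [√400 × 0.10 − 1.960 × √0.4982] / √0.4932 = (2.000 − 1.3834) / 0.7023 = 0.878, so power is 81.0%.
- Continuity-corrected: solving the formula in step 1 for n when n_c = 400 gives √n = 20 − 1/(0.10 × 20) = 19.5. Then z = (1.950 − 1.3834) / 0.7023 = 0.807, so power is 79.0%. The same calculation at 410 per group gives 80.0%.

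**The case against.** The arithmetic is not open to dispute, but its importance is.

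- **Power under the planned test.** Section 6 names the chi-squared test and logistic regression and mentions no continuity correction. Without one, 390 per group suffice, and the 400 left after 20% loss give 81.0%. On that basis power does not fall below 80%. The correction is inferred because it reproduces 410; the protocol does not state it. This stands, and it is why the 79.0% must be labelled as conditional. It does not rescue the paragraph, because an uncorrected calculation would have given a minimum of 780. The protocol states 820 and misses it at its own loss rate.
- **Size.** A shortfall of 20 in 820 is 2.4%, worth about one point of power on the less favourable reading. The 20% itself is given without a source. This also stands: the error does not threaten the study.
- **Precision.** The 42% and 52% refer to a single all-or-none composite, whereas section 5.3.1 names two co-primary outcomes and section 6 gives no rates for either. Any restated power therefore applies to the single composite only. That limits what the power figure means, but it does not affect the inflation error.

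**Conclusion.** The concern holds. The total of 984 is not 820 inflated for 20% loss; the correct total is 1025, or 1026 with equal groups. The planned 1000 leaves 800 evaluable at the stated loss, 20 below the stated minimum. The enrolment is 25 to 26 patients short of what the protocol's own inputs require, and it tolerates 18% loss instead of 20%.

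The shortfall against 820 rests only on figures in the protocol and on reading the 20% as a share of those enrolled. The drop in power from 80% to 79.0% also assumes the continuity-corrected formula; an uncorrected test keeps 81.0%. Both power figures treat women and men as independent groups. If matched pairs were analysed as pairs, the loss of either member would remove the pair and the effective loss would be larger. The protocol does not state a paired analysis, so this is not counted here.

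The fault is a wrong figure with a minor consequence. It should be corrected because it is the stated basis for the study's size.

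**What to change.** Keep 1000 and correct the sentence in section 6. Suggested content: 820 / 0.80 = 1025; with 1000 enrolled, the minimum of 820 is met if loss to follow-up is at most 18%; at 20% loss, 400 per group remain, giving 79% power with a continuity correction (81% without) for 42% versus 52% on the all-or-none composite. State there that the calculation is two-sided and continuity-corrected, if the authors confirm it, so that 410 can be reproduced.

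This costs one sentence and no patients; the tolerated loss or the stated power becomes slightly less favourable. If the authors prefer to keep both the 820 and the 20% loss, enrolment would have to rise to 1026 (513 per group), which is 26 more than planned.

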5.3.3. Pre-defined exploratory outcomes

- Composite outcome of adherence to all secondary CV prevention recommendations 6 months after discharge (all-or-none composite outcome with a binary response)

- Percentage of patients achieving optimal (guidelines-recommended) control of all individual CV risk factors (LDL-cholesterol levels, blood pressure levels, HbA1c levels, smoking, levels of physical activity/sedentary life)
- 12-month incidence of the composite clinical endpoint: All-cause death, all-cause rehospitalization, and all-cause emergency department visits
- Use of healthcare resources at 12 months, including: days hospitalized (re-hospitalizations), number of ED visits, number of cardiac rehabilitation sessions, number of outpatient specialist visits, and number of urgent PCI procedures).
- Assessment of the main predictors of adherence with secondary prevention recommendations in women (biological, disease-related, pharmacological, socio-economic, psychological, gender)
- Composite outcome of adherence to all secondary pharmacological CV prevention recommendations 12 months after discharge, using pharmacy dispensation records.
- In addition, data on changes in dose or drug will be collected to analyze their influence on adherence.
- Evaluation of each individual components of the composite of adherence to secondary CV prevention recommendations 6 and 12 months after discharge (these recommendations will be given to all patients at discharge):
 - Pharmacological therapies
 - Diet
 - Physical activity and
 - Participation in cardiac rehabilitation programs
- Percentage of patients achieving optimal (guidelines-recommended) control of all individual CV risk factors:
 - LDL-cholesterol levels
 - Blood pressure levels
 - HbA1c levels
 - BMI
 - Smoking

- Levels of physical activity/sedentary life
- Diet
- Composite endpoint of cardiovascular death, rehospitalization, and emergency department visits for cardiovascular causes, and urgent coronary revascularization.
- Effect of delays on return to work on adherence to cardiac rehabilitation and other secondary prevention measures.

OUTCOME METRICS

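### A fixed 12-month follow-up is assumed for every patient although 20% loss is expected; this suits 12-month adherence status but not the clinical-event outcomes

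*Protocol*

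**What the plan says.** Protocol section 6 plans logistic regression for binary outcomes and then states: "All subjects will be assumed to have a fixed follow-up (12±1 month"). The Statistical analysis paragraph of the Summary repeats the assumption directly after extending logistic models from the primary outcome to the other outcomes. For other types of outcome, section 6 says: "Linear, multinomial or ordinal regression models would be used".

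The sample-size paragraph of the same section says: "With the consideration of 20% of lost to follow-up (discontinuations) the total sample size is 984 patients".

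The outcomes that depend on time at risk are:

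- In section 5.3.3: "12-month incidence of the composite clinical endpoint: All-cause death, all-cause rehospitalization, and all-cause emergency department visits". That section lists it as exploratory; the Summary lists it among the secondary end-points.
- Also in section 5.3.3, resource use, including "days hospitalized (re-hospitalizations), number of ED visits, number of cardiac rehabilitation sessions".
- In item f of the outcome metrics (section 5.3), major cardiovascular events at 6 and 12 months and their components.

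For resource use and costs, item h of the outcome metrics and the end of section 6 name the COHERENT model. The protocol mentions no censoring, time at risk or person-time for any of these outcomes.

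**The concern.** The two statements fit together for an adherence status measured at 12 months. A patient either has that measurement or does not, and the difficulty is then missing data. They do not fit for events that accrue. A patient last seen at month 3 has contributed three months at risk, and the fixed-follow-up assumption credits twelve. This is a rule that the protocol states, not a detail left for a later plan.

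At stake is the third hypothesis in section 2 (more clinical events or healthcare use in women) and objectives 2b and 2c in section 3. Absolute 12-month risks could be misread. If loss differs between women and men, part of that difference could appear as a sex difference in outcome.

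**Working it through.** **The plan's own figure.** Inputs from section 6: "The recommendations compliance was estimated as 42% for women and 52% for men"; "An α error of 0.05 and a β error of 0.20 were considered for the sample size". Taking a two-sided test:

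- Without continuity correction: n = [1.960·√(2·0.47·0.53) + 0.842·√(0.42·0.58 + 0.52·0.48)]² / 0.10² = 390 per group.
- With continuity correction: (n/4)·[1 + √(1 + 4/(n·0.10))]² = 410 per group, 820 in total, as stated.
- 820 × 1.2 = 984, as stated. Dividing by 0.8 would give 1025, which is a separate matter.

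So 20% is the protocol's own planning figure for loss, about 200 of 1000 patients. It is not split by sex.

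**Assumed inputs (not in the protocol).** True 12-month event risk p from 10% to 50%; constant hazard; a fraction L lost evenly over 12 months; 500 per group; lost patients kept as if fully followed, with only the events seen before loss counted.

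**Formula.** λ = −ln(1 − p). The chance that a lost patient's event is seen before loss is e = 1 − p/λ. Observed risk = (1 − L)·p + L·e.

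Example, p = 0.40 and L = 0.20: λ = 0.511; e = 1 − 0.40/0.511 = 0.217; observed risk = 0.80·0.40 + 0.20·0.217 = 0.363.

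**Equal 20% loss**

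| True risk | Read as | Ratio |
|---|---|---|
| 10% | 9.0% | 0.902 |
| 20% | 18.1% | 0.904 |
| 30% | 27.2% | 0.906 |
| 40% | 36.3% | 0.908 |
| 50% | 45.6% | 0.911 |

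If all loss fell at the start, the reading would be 20% low (0.80·p). Observed person-time is 1 − 0.20/2 = 90% of that assumed.

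The sex comparison barely moves: an assumed true 36% versus 30% (OR 1.31) gives OR 1.30.

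**Unequal loss, 25% in women and 15% in men, no true difference.** The false gap is (0.25 − 0.15)·(p − e).

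| True risk | Women | Men | Gap (points) | OR | Two-sided rejection probability |
|---|---|---|---|---|---|
| 30% | 26.5% | 27.9% | −1.4 | 0.93 | 7.9% |
| 40% | 35.4% | 37.3% | −1.8 | 0.92 | 9.2% |
| 50% | 44.5% | 46.7% | −2.2 | 0.92 | 10.8% |

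Reversing the split reverses the sign (OR 1.07 to 1.09 over the same risks). With a true 36% versus 30%, loss of 25/15 gives OR 1.21 and loss of 15/25 gives OR 1.40. A true 48% versus 40% under 25/15 loss reads as 42.6% versus 37.3%: 8 points become 5.4 (from unrounded values).

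**Other ways to handle lost patients, at 20% loss**

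- Drop only those lost without an event: observed risk = [(1 − L)·p + L·e] / [1 − L·(1 − e)]. A true 30% reads as 32.7%, and a true 40% as 0.3634/0.8434 = 43.1%. At 40% with 25/15 loss the readings are 44.0% and 42.2%, so women now look worse.
- Exclude everyone lost: 30% stays 30% and 40% stays 40% if loss is unrelated to outcome, but events already observed are discarded.

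**The case against.** The strongest reply is that the sentence gives the common planned horizon as the reason for analysing a binary status, and does not say that a lost patient is scored event-free. Detailed handling of losses commonly belongs in an analysis plan, which is not shown. Part of this stands: the direction of any bias is not fixed by the text. But the sentence covers all subjects, and the Summary places it after extending the models to the other outcomes. As written, it misstates time at risk.

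Four stronger readings are tempting, and the protocol does not support them.

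- *Event risks will be understated, and any sex difference in loss will become a false difference in outcome.* This holds only if lost patients stay in the denominator as fully followed. Exclusion under non-informative loss gives no bias, and dropping only event-free losses over-reads risk.
- *A fifth of patients will lack clinical-event data.* The 20% is a sample-size allowance for the adherence composite. Section 7 allows some variables to be collected automatically from electronic systems, so events might be found after contact is lost. The protocol does not say so for clinical events; it describes checking records only for pharmacy dispensation.
- *Resource use has no method beyond linear, multinomial and ordinal regression.* The COHERENT model is named for it. How that model treats incomplete follow-up cannot be judged from the protocol.
- *The one-month window alone distorts the result.* Under constant hazard a 40% risk would be 37.4% at 11 months and 42.5% at 13, but only if everyone sat at one extreme, and nothing suggests that timing differs by sex.

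The reply is also right that section 5.3.3 ranks these outcomes as exploratory and that the co-primary outcomes are unaffected by the time-at-risk argument.

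**Conclusion.** The point holds for the clinical-event outcomes and, more weakly, for resource counts. The protocol assumes complete follow-up in the same section that plans for 20% loss, and that assumption is unsuited to outcomes that accumulate over time. Taken literally, event risk reads about 9-10% low in relative terms. Equal loss leaves the sex comparison almost intact. A 10-point difference in loss shifts a null comparison by 1.4-2.2 points for true risks of 30-50%, in either direction.

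These sizes rest on assumed event rates, constant hazard, evenly spread loss and lost patients kept as fully followed. The protocol supplies only the 20%. The result is a modest, conditional distortion of outcomes that section 5.3.3 calls exploratory but that carry one of the three named hypotheses. It is not a demonstrated bias, and it does not touch the choice of logistic regression for 12-month adherence. The correction is worth making because it is cheap and removes the dependence on an unstated rule for lost patients.

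**What to change.** - In section 6 and the Summary, limit the fixed-follow-up sentence to the 12-month adherence outcomes.
- Analyse the clinical composites as time to first event: Kaplan-Meier 12-month risk by sex and a Cox model that accounts for the matching, censored at last contact or last record check, whichever the protocol defines as the end of event ascertainment.
- For composites restricted to cardiovascular causes, report cumulative incidence with non-cardiovascular death as a competing event.
- For resource use, keep the COHERENT model and express counts per observed follow-up time, for example with a log person-time offset in any count regression. Follow-up shortened by death should be reflected as well.
- Report loss to follow-up by sex. Censoring removes the bias only if loss is non-informative.

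Cost: dates of events and of last contact or record check must be in the database, and there is slightly more analysis work. No extra patients are needed.

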However, most comparisons between women and men with AMI are hampered by the major differences in the epidemiology and pathophysiology of AMI,¹³ including the older age of women, their greater comorbidity (particularly, renal disease),¹¹ increased risk of adverse effects with therapies (i.e. bleeding)⁴⁹ and the different proportion of different AMI types (i.e. women presenting more often with type-2 AMI or with non-obstructive coronary artery disease),^{15,55,61} which has therapeutic and prognostic implications. These differences need to be accounted for to improve the accuracy of comparisons and define more clearly the role of sex and gender on the management and outcomes of AMI.⁴⁶

Gender and determinants of adherence to evidence-based therapies after AMI

Age, gender, the presence of comorbidities and polypharmacy are factors that predict adherence to secondary prevention therapies⁶². Women with AMI have been found to have differences in adherence compared with men, with lower adherence to P2Y₁₂ inhibitors (i.e. clopidogrel)⁶³ or a 10% greater probability of non-adherence to statins.⁶⁴ In a study with 148,654 patients with AMI, who had received secondary prevention measures in accordance with the clinical guidelines (loading dose of antiplatelets and chronic doses of aspirin, beta-blockers and ACE inhibitors in patients with AMI and reduced left ventricular ejection fraction, lipid-lowering drugs and medical advice smoking cessation) female gender was associated with poorer adherence on all measures⁶⁵. However, a recent meta-analysis showed a lower adherence to lipid-lowering drugs (OR = 0.87, 95% CI 0.82-0.92) with no differences in the other three major pharmacological groups of secondary prevention (ACE inhibitors/ARA-II, beta-blockers and antiplatelets) in women post-MI,⁶⁶ but the role of the differences in age and comorbidities in these results is unknown. Regarding the adherence to non-pharmacological secondary prevention measures, registries and observational studies have observed that men are less likely to achieve blood pressure goals than women.⁶⁷ The results of the EUROASPIRE V survey also reveal that women change their healthy food habits in compliance with the recommendations, more frequently than men do.⁶⁸

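### Men are matched to women on age, ECG type and hospital, but the covariate rule gives hospital no evident route into the models, at a small cost in power

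*Protocol*

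**What the plan says.** Protocol section 4.1 sets the design: "Men will be recruited subsequently as the comparison group, with 1:1 matching for age and ECG presentation". The comparator cohort is described as "500 age (± 2 years) and ECG (STEMI/NSTEMI) locally matched men discharged alive", and the place of matching is explicit: "Matching will be performed locally, in each study site (hospital"). There are therefore three matching factors: age, ECG type and hospital.

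Section 6 compares women and men by logistic regression for binary outcomes and adds: "Multivariate adjusted models will be used to address any potential confounding in the associations between sex and each of the outcomes". It then gives the rule for what enters these models: "Covariates will be selected based on their pre-defined clinical value and the unbalances observed across groups in the univariate analyses". It names no stratified, mixed, clustered or hospital-adjusted form.

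Later in section 6 a separate predictive model has its own list: "Candidate predictors are classified as biological factors (age, sex, risk factors, comorbidities), disease-related (type of MI: STEMI/NSTEMI" and so on. That list contains age, type of infarction and zip code, but not hospital. Regional variability is mentioned only as something to explore.

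**The concern.** A factor used for matching is balanced between the sexes by construction, yet it may still predict adherence. A rule that looks for imbalance will tend to pass over exactly these factors. When a balanced factor that predicts outcome is left out, the usual standard error treats the two groups as independent and is too large. The test is then conservative and part of the efficiency bought by matching is not used.

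The gap is mainly hospital. Age and ECG type have a route through clinical value; section 1 itself says of adherence: "Age, gender, the presence of comorbidities and polypharmacy are factors that predict adherence to secondary prevention therapies". Hospital has no comparable route. Yet one component of the composite is attendance at 80% or more of scheduled cardiac rehabilitation sessions, which plausibly varies by site, and the 25 hospitals were chosen partly to explore regional variability.

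Logistic regression is not the fault, and matching controls confounding by these factors without a paired model. What is at stake is a little power and a correctly reported standard error, not bias or inflated type I error.

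**Working it through.** **Inputs from protocol section 6.** 42% (women) versus 52% (men); α = 0.05; power 80%; 410 per group; 20% loss; 500 per sex enrolled; 25 hospitals.

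**The plan's own figure.** The two-sided, two-proportion formula for independent groups gives 390 per group, and 410 with continuity correction, which matches the protocol exactly. The sample size therefore takes no credit for matching.

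**Assumption.** The protocol gives no within-pair correlation ρ. A range of 0 to 0.10 is used.

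**1. Upper bound: no matching factor in the model.** With 20% independent loss, 500 × 0.8 = 400 remain per sex and 500 × 0.8 × 0.8 = 320 pairs stay complete.

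- Reported SE of the risk difference = √[(0.42·0.58 + 0.52·0.48)/400] = 0.03511
- True variance = SE² − 2·320·ρ·√(0.42·0.58·0.52·0.48)/400²
- Type I error = 2·[1 − Φ(1.96·SE/true SE)]
- Power as planned = Φ[(0.10 − 1.96·SE)/true SE]
- Power with the correct SE = Φ(0.10/true SE − 1.96)

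| ρ | True SE | Type I error | Power, factors omitted | Power, correct SE | Loss (points) |
|---|---|---|---|---|---|
| 0 | 0.03511 | 5.0% | 81.3% | 81.3% | 0 |
| 0.02 | 0.03483 | 4.8% | 81.5% | 81.9% | 0.4 |
| 0.05 | 0.03440 | 4.5% | 81.8% | 82.8% | 1.0 |
| 0.10 | 0.03368 | 4.1% | 82.3% | 84.4% | 2.1 |

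**2. What remains when age and ECG type are already in the model.** Simulation: 25 hospitals × 20 pairs, men's age within ±2 years (assumed SD 12), 20% independent loss, incomplete pairs kept, Wald tests, 4000 runs per setting. Effects were assumed on the logit scale as hospital SD / age effect per SD / ECG effect.

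| Assumed effects | Resulting ρ | Power, age + ECG | Power, plus hospital random intercept |
|---|---|---|---|
| 0 / 0 / 0 | 0 | 80.8% | 80.9% |
| 0.25 / 0.2 / 0.2 | 0.025 | 82.0% | 82.2% |
| 0.4 / 0.3 / 0.2 | 0.055 | 82.0% | 83.1% |
| 0.5 / 0.4 / 0.3 | 0.087 | 82.9% | 84.6% |
| 0.6 / 0 / 0 | 0.073 | 81.6% | 83.7% |

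In the same order of rows, type I error was 5.1, 5.1, 5.0, 4.8 and 4.5% without hospital, 5.1, 5.2, 5.3, 5.3 and 5.6% with the random intercept, and 5.4, 5.8, 5.7, 5.7 and 5.9% with hospital as fixed effects (Monte Carlo SE about 0.35 points).

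**3. Separate simulation.** 25 hospitals × 16 complete pairs, 3000 runs, plain logistic model against one with hospital effects, by hospital intraclass correlation (ICC) on the logit scale:

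| ICC | Power, plain | Power, with hospital | Type I error, plain | Type I error, with hospital |
|---|---|---|---|---|
| 0 | 81.5% | 81.7% | 5.1% | 5.1% |
| 0.02 | 82.5% | 82.9% | 4.6% | 4.8% |
| 0.05 | 81.4% | 83.3% | 4.5% | 5.1% |
| 0.10 | 81.9% | 84.2% | 4.1% | 4.9% |
| 0.20 | 82.7% | 87.1% | 2.8% | 4.6% |

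**4. What changes and what does not.** At ρ = 0.087 the actual SD of the estimated risk difference is 0.033 in every model. The mean reported SE is 0.0350 with no covariates, 0.0343 with age and ECG type, and 0.0330 with hospital added as fixed effects. The estimate is no more precise; omitting the factors overstates its SE. On the log-odds scale the SE rises (0.143, then 0.146, then 0.150 with hospital) because the odds ratio becomes conditional and moves further from 1, and power still increases.

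**The case against.** The strongest reply is that this is an omission of a kind often left to a statistical analysis plan. Clinical value is an open-ended criterion, hospital is nowhere barred, the list of candidate predictors is not exhaustive and belongs to another model, and uneven loss to follow-up could unbalance hospital and let it in. All of that is true, and it is why the point is that hospital has no evident route, not that it is excluded. But section 6 does more than stay silent: it states a selection rule, and one half of that rule works against factors that the design has balanced.

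Second, the effect is small, conservative, and zero if ρ is 0. This stands in full.

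Third, part of the simulated gain in the second step may come from a slightly liberal test. Rescaling both tests to an exact 5% level by normal approximation cuts the gain to about 0.5 points at ρ 0.055, 1.1 at 0.087 and 0.9 at 0.073. Those corrections rest on type I errors with a Monte Carlo SE of about 0.35 points. In a further 20,000-run simulation with hospital SD 0.6, a hospital-stratified test had type I error 5.1% and power 84.0%, against 4.3% and 82.1% for the plain test. The third step likewise shows the gain with type I error no higher than 5.1%. The objection is therefore largely noise.

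**Conclusion.** The concern holds, as a minor but real inefficiency. The matching factors, and hospital above all, should not depend on a rule that looks for imbalance. Over an assumed ρ of 0 to 0.10 the cost is 0 to about 2 points of power, with type I error between 5.0% and 4.1% when no matching factor is modelled; the cost is generally smaller when age and ECG type are already included. At a hospital ICC of 0.20 on the logit scale the loss would be about 4 points. Planned power of about 80% is kept throughout, and no result becomes invalid. The sizes rest on assumed correlations and, in the second step, on assumed age, ECG and hospital effects, because the protocol gives none.

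**What to change.** In section 6, state that every model comparing women and men includes age, ECG type and hospital regardless of observed imbalance, and that patients whose matched partner is lost stay in the analysis. Enter hospital as a random intercept: this matters most for rare outcomes, and for the primary outcome it was slightly better calibrated than 24 fixed effects (type I error 5.1 to 5.6% against 5.4 to 5.9%). Pair-clustered robust standard errors, with the pair identifier recorded, are an optional addition.

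State also that the adjusted odds ratio is conditional on these factors and that its confidence interval need not be narrower than the unadjusted one. The gain is in power and in the reported SE of a marginal contrast such as the risk difference.

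The cost is two sentences and slightly more analysis work, with a change from a marginal to a conditional odds ratio whose interval may be slightly wider on the log scale. Recruitment and sample size are unaffected.
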